#### 6.2.2.2. Laboratory data

Missing laboratory results (including immunological data) will not be replaced.

Missing laboratory results (including immunological data) will not be replaced.

Haematology/chemistry laboratory data requiring grading as per the protocol toxicity grading scale, which is based upon the FDA Toxicity Grading Scale for Healthy Adult and Adolescent Volunteers Enrolled in Preventive Vaccine Clinical Trials, may have more decimals than expected or may require conversion to the unit associated to the grade, leading to more decimals than expected.

In order to determine the grading the following rule will be used:

- 1. In case a conversion is needed, the original results will be used for the conversion without a previous rounding.
- 2. In case an approximation is needed to determine the grading, the result (or the result divided by the upper limit of the normal range (ULN), depending on the test) expressed in the expected unit will be rounded to the number of decimals used for the grading.

Serum **	Mild (Grade 1)	Moderate (Grade 2)	Severe (Grade 3)	Potentially life threatening (Grade 4)***
BUN mg/dL	23 – 26	27 – 31	> 31	Requires dialysis
Creatinine mg/dL	1.5 – 1.7	1.8 – 2.0	2.1 – 2.5	> 2.5 or requires dialysis
Liver function tests – ALT, AST increase by factor	1.1 – 2.5 x ULN	2.6 – 5.0 x ULN	5.1 – 10 x ULN	> 10 x ULN
ALP – increase by factor	1.1 – 2.0 x ULN	2.1 – 3.0 x ULN	3.1 – 10 x ULN	> 10 x ULN
Bilirubin – when liver function test is normal; increase by factor	1.1 – 1.5 x ULN	1.6 – 2.0 x ULN	2.0 – 3.0 x ULN	> 3.0 x ULN
Bilirubin – when accompanied by any increase in liver function test increase by factor	1.1 – 1.25 x ULN	1.26 – 1.5 x ULN	1.51 – 1.75 x ULN	> 1.75 x ULN

# Table 6Toxicity grading scales for biochemistry parameters evaluated in the
current study\*

ALP: Alkaline phosphatase; ALT: Alanine aminotransferase; AST: Aspartate aminotransferase; BUN: Blood urea nitrogen; ULN: upper limit of normal.

\* Toxicity grading taken from FDA guidance for industry: Toxicity grading scale for healthy adult and adolescent volunteers enrolled in preventive vaccine clinical trials [Food and Drug Administration, 2007].

\*\* The laboratory values provided in the tables serve as guidelines and are dependent upon institutional normal parameters. Institutional normal reference ranges should be provided to demonstrate that they are appropriate.

\*\*\* The clinical signs or symptoms associated with laboratory abnormalities might result in characterization of the laboratory abnormalities as potentially life-threatening (Grade 4). For example, a low sodium value that falls within a Grade 3 parameter (125-129 mE/L) should be recorded as a Grade 4 hyponatremia event if the participant had a new seizure associated with the low sodium value.

Hematology**	Mild (Grade 1)	Moderate (Grade 2)	Severe (Grade 3)	Potentially life- threatening (Grade 4)
Hemoglobin (Female) - gm/dL	11.0 – 12.0	9.5 – 10.9	8.0 – 9.4	< 8.0
Hemoglobin (Female) change from baseline value - gm/dL	Any decrease – 1.5	1.6 – 2.0	2.1 – 5.0	> 5.0
Hemoglobin (Male) - gm/dL	12.5 – 13.5	10.5 – 12.4	8.5 – 10.4	< 8.5
Hemoglobin (Male) change from baseline value – gm/dL	Any decrease – 1.5	1.6 – 2.0	2.1 – 5.0	> 5.0
WBC Increase - cell/mm 	10,800 – 15,000	15,001 – 20,000	20,001 – 25,000	> 25,000
WBC Decrease - cell/mm 	2,500 – 3,500	1,500 – 2,499	1,000 – 1,499	< 1,000
Lymphocytes decrease - cell/mm 	750 – 1 000	500 – 749	250 – 499	< 250
Neutrophils decrease - cell/mm 	1,500 – 2,000	1,000 – 1,499	500 – 999	< 500
Eosinophils - cell/mm 	650 – 1 500	1,501 – 5,000	> 5,000	Hypereosinophilic
Platelets decreased - cell/mm 	125,000 – 140,000	100,000 - 124,000	25,000 – 99,000	< 25,000
Prothrombin Time – increase by factor	1.03 – 1.10 x ULN	1.11 – 1.20 x ULN	1.21 – 1.25 x ULN	>1.25 x ULN

# Table 7Toxicity grading scales for hematology parameters evaluated in the
current study\*

ULN: Upper limit of the normal range; WBC: White blood cell.

\* Toxicity grading taken from FDA guidance for industry: toxicity grading scale for healthy adult and adolescent volunteers enrolled in preventive vaccine clinical trials [Food and Drug Administration , 2007].

\*\* The laboratory values provided in the tables serve as guidelines and are dependent upon institutional normal parameters. Institutional normal reference ranges should be provided to demonstrate that they are appropriate.

#### 6.2.2.3. Daily recording of solicited events

#### 6.2.2.3.1. Studies with electronic diaries

For studies using electronic diaries for the collection of solicited events, a solicited event will be considered present only when a daily recording of grade 1 or more is present.

#### 6.2.2.4. Unsolicited adverse events

Unsolicited AE summaries are including SAEs unless specified otherwise.

Missing severity, relationship with study intervention, and outcome of unsolicited AEs will not be replaced and will appear as 'UNKNOWN' when displayed in a statistical output.

## 6.2.3. Data derivation

## 6.2.3.1. Weight

Weight will be presented in kilograms. Weights reported in pounds will be converted as follows:

Weight in kilograms = Weight in pounds / 2.2

## 6.2.3.2. Height

Height will be presented in centimeters. Heights reported in feet and inches will be converted as follows:

Height in centimeters = Height in inches x 2.54

## 6.2.3.3. Body mass index (BMI)

BMI will be calculated as follows:

 $BMI = (Weight in kilograms) / (Height in meters)^2$ 

#### 6.2.3.4. Temperature

Temperatures will be presented in degrees Celsius (°C). Temperatures reported in degrees Fahrenheit (°F) will be converted as follows:

Temperature (Celsius) = ((Temperature (Fahrenheit) - 32) x 5)/9

## 6.2.3.5. Numerical serology results

Numerical serology results will be derived from the content of IS.ISORRES in the SDTM dataset. For assays with a specific cut-off, the following derivation rules apply:

IS.ISORRES	Derived value
"NEG", "-", or "(-)"	cut-off/2
"POS", "+", or "(+)"	cut-off
"< value" and value is <= assay cut-off*	cut-off/2
"< value" and value is > assay cut-off	value
"> value" and value is < assay cut-off	cut-off/2
"> value" and value is >= assay cut-off	value
"value" and value is < cut-off	cut-off/2
"value" and value is >= cut-off	value
All other cases	missing

\* Lower limit of quantitation (LLOQ)

#### LLOQs for different assays

Antigen	Assay and assay unit	LLOQ
SARS-CoV-2 Spike BA.5	PNA (NT50)	10
SARS-CoV-2 Spike D614G	PNA (NT50)	10
SARS-CoV-2 Spike Wuhan (D614)	IgG (AU/mL)	360
SARS-CoV-2 Spike D614G	IgG (AU/mL)	410
SARS-CoV-2 Spike XBB.1	IgG (AU/mL)	120
SARS-CoV-2 Spike B.1.617.2 (Delta)	IgG (AU/mL)	790
SARS-CoV-2 Spike XBB.1.5	IgG (AU/mL)	230
SARS-CoV-2 Spike BA.2.75	IgG (AU/mL)	200
SARS-CoV-2 Spike XBB.1.16	IgG (AU/mL)	170
SARS-CoV-2 Spike B.1.1.529 (BA.1)	IgG (AU/mL)	150
SARS-CoV-2 Spike BQ.1	IgG (AU/mL)	170
SARS-CoV-2 Spike BA.5	IgG (AU/mL)	220
SARS-CoV-2 Spike Wuhan (D614)	Polypositive CD4+ T (10E6 cells)	590
SARS-CoV-2 Spike Wuhan (D614)	Polypositive CD8+ T (10E6 cells)	590
SARS-CoV-2 Spike Wuhan (D614)	CD4+ expressing at least IFN- γ (10E6 cells)	N/A
SARS-CoV-2 Spike Wuhan (D614)	CD4+ expressing at least IL-13 (10E6 cells)	N/A
SARS-CoV-2 Spike Wuhan (D614)	CD4+ expressing at least IL-17 (10E6 cells)	N/A
SARS-CoV-2 Spike BA.5	Polypositive CD4+ T (10E6 cells)	590
SARS-CoV-2 Spike BA.5	Polypositive CD8+ T (10E6 cells)	590
SARS-CoV-2 Spike BA.5	CD4+ expressing at least IFN- γ (10E6 cells)	N/A
SARS-CoV-2 Spike BA.5	CD4+ expressing at least IL-13 (10E6 cells)	N/A
SARS-CoV-2 Spike BA.5	CD4+ expressing at least IL-17 (10E6 cells)	N/A

#### 6.2.3.6. Geometric mean titres (GMTs) and GMCs

Geometric Mean Titre (GMT) or GMC calculations are performed by taking the inverse logarithm of the mean of the log titre or concentration transformations. Non quantifiable antibody titres or concentrations will be converted as described in Section 6.2.3.5 for the purpose of GMT/GMC calculation. The cut-off value is defined by the laboratory before the analysis. If not otherwise specified, the cut-off refers to the LLOQ.

#### 6.2.3.7. Onset day

The definition of onset day for an event (e.g. AE, concomitant medication/vaccination) is the number of days between the last study dose and the start date of the event. This is 1 for an event occurring on the same day as a study dose (and reported as starting after study dose).

#### 6.2.3.8. Duration of events

The duration of an event with a start and end date will be the difference between the start and end date plus one day, i.e. an event that starts on 03MAR2018 and ends on 12MAR2018 has a duration of 10 days.

#### 6.2.3.9. Counting rules for combining solicited and unsolicited adverse events

For output combining solicited and unsolicited AEs, all SAEs might have to be considered general events since the administration site flag is not included in the expedited adverse event CRF pages.

Multiple events with the same preferred term which start on the same day are counted as only one occurrence.

#### 6.2.3.10. Counting rules for occurrences of solicited events

When the occurrences of solicited events are summarized, each event recorded as having occurred during a specific period will be counted as only one occurrence regardless of the number of days on which it occurs.

#### 6.2.3.11. AESIs

GSK MedDRA queries will be used to identify AESI:

- PIMD: refer to Table 12 from the protocol
- Severe hypersensitivity (including anaphylaxis): Grade 3 unsolicited AEs under MedDRA SMQ hypersensitivity, narrow search (includes anaphylaxis), with an onset within 24 hours after dosing
- Myocarditis/Pericarditis. In addition to identification based on the medical and scientific judgement of the investigator, the following list of MedDRA SMQs will be used: Cardiac arrhythmia, Cardiac failure, Cardiomyopathy, Ischaemic heart disease, Non-infectious myocarditis/ pericarditis, narrow search.
- Virologically confirmed COVID-19 cases: In addition to identification based on the medical and scientific judgement of the investigator, AEs under MedDRA SMQ COVID-19, narrow search will be used

This PIMD, Virologically confirmed COVID- 19 cases, Myocarditis and Pericarditis queries may be revised based on MedDRA dictionary.

AESI summaries will include AE identified by either the investigator or the MedDRA queries.

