#### 8.4.4.2. Other AESIs

- Myocarditis and pericarditis
- Virologically confirmed COVID-19 cases
- Anaphylaxis or severe hypersensitivity within 24 hours after study vaccination

When there is enough evidence to make any of the above diagnoses, the AE must be reported as AESI. Symptoms, signs or conditions which might (or might not) lead to one of the above diagnoses, should be recorded and reported as AEs but not as AESI until the final or definitive diagnosis has been made, and alternative diagnoses eliminated or shown to be less likely.

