### Clinical myocarditis/pericarditis:

The participants reporting acute chest pain, shortness of breath or other signs/symptoms of myocarditis/pericarditis within 6 weeks after vaccination must be evaluated by a cardiologist with evaluation and management following current practice guidelines (e.g., American heart association or local standard of care).

The changes suggestive of myocarditis and pericarditis (but not limited to) are listed below:

- EKG changes:
  - ST segment or T wave abnormalities (elevation or inversion)
  - Paroxysmal or sustained atrial or ventricular arrhythmias
  - AV nodal conduction delays or intraventricular conduction defects.
  - An abnormal troponin I value (> 2 ULN of baseline value) that is confirmed abnormal on repeat testing.
- Cardiac imaging:
  - Echocardiogram: New left or right ventricular function abnormalities including: segmental wall motion abnormalities; decreased ejection fraction (EF <55% for ≤54 yrs; or <50% for >55 yrs); global systolic or diastolic function depression/abnormality; ventricular dilation or wall thickness change; pericardial effusion or intracavitary thrombi
  - Cardiac MRI: Patchy edema on T2 weighted images or late gadolinium enhancement on T1 weighted images with increased enhancement ratio between myocardial skeletal muscle involving ≥1 non-ischemic regional distribution with recovery

The participants will be followed-up until the resolution of symptoms and/or cardiac troponin levels return back to normal.

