### **Events Meeting the AE Definition**

- Any abnormal laboratory test results (hematology, clinical chemistry, or urinalysis) or other safety assessments (e.g., EKG, radiological scans, vital signs measurements), including those that worsen from baseline, considered clinically significant in the medical and scientific judgment of the investigator (i.e., not related to progression of underlying disease).
- Exacerbation of a chronic or intermittent pre-existing condition including either an increase in frequency and/or intensity of the condition.
- New condition detected or diagnosed after study intervention administration even though it may have been present before the start of the study.
- Signs, symptoms, or the clinical sequelae of a suspected intervention- intervention interaction.
- Signs, symptoms, or the clinical sequelae of a suspected overdose of either study intervention or a concomitant medication. Overdose per se will not be reported as an AE/SAE unless it is an intentional overdose taken with possible suicidal/self-harming intent. Such overdoses should be reported regardless of sequelae.
- Events that occur as a result of protocol-mandated procedures (i.e. invasive procedures, modification of participant's previous therapeutic regimen).

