• To describe cell-mediated immune responses induced by the mRNA-CR-04 vaccine up to study conclusion.	
 
Frequency of CD4+/CD8+ T-cells specific for S protein encoded by the vaccine SARS-CoV-2 and WT strains measured by intracellular cytokine staining assay at each time point (D1, D15, D31, M6).
 
Cellular immune responses including, but not limited to Th1 and Th2 profiles as determined by flow cytometry using ICS at each time point (D1, D15, D31, M6).
 

• To describe the incidence of confirmed symptomatic and asymptomatic SARS- CoV-2 infection.	
 
Percentage of laboratory-confirmed (N protein seroconversion) asymptomatic SARS-CoV-2 infection at each time point (D1, D15, D31, M6).
 
Percentage of laboratory-confirmed (RT-PCR) symptomatic SARS-CoV-2 infection at D8, D15, as well as at unscheduled visits.
 

• To evaluate the genetic sequence of SARS-CoV-2 variant S protein in confirmed (RT-PCR) SARS-CoV-2 positive participants.	
 
Comparison of SARS-CoV-2 S protein genetic sequence of viral isolates (when available) to the vaccine mRNA sequence
 
Identification of SARS-CoV-2 variants.
 

• To further characterize the humoral response (including, but not limited to functionality of antibodies) and cellular response, specific for the vaccine encoded SARS-CoV-2, WT and other relevant strains.	
 
S-specific responses at D1, D15, D31, M6
 
Other read-outs may be performed if deemed necessary.
 

Ab: Antibody; AE: Adverse event; AESI: Adverse events of special interest; D: Day; GMR: Geometric mean ratio; GMT: Geometric mean titer; ICS: intracellular cytokine staining; IgG: Immunoglobulin G; M: Month; MAAE: Medically attended adverse events; N: Nucleocapsid; pIMD: potential Immune-mediated disease; RT-PCR: Real-time polymerase chain reaction; S: Spike; SAE: Serious adverse event; VAED: Vaccine associated enhanced disease; WT: Wild type.

\*AESI include pIMDs, myocarditis/pericarditis, virologically confirmed COVID-19 cases and anaphylaxis or severe hypersensitivity within 24 hours after study vaccination (Protocol Section 8.4.4).

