## 4.2.1.3. Adverse Events of Special Interest

The analysis of adverse events of special interest will be performed on Exposed Set.

For adverse events of special interest (AESI) collected up to study conclusion (M6), the following will be considered for the purpose of analyses:

- pIMDs
- Anaphylaxis or severe hypersensitivity reactions within 24 hours after study intervention administration
- Pericarditis and myocarditis.
- Virologically confirmed COVID-19 cases (Protocol Section 8.4.4.2.2)

The summary of event characteristics will be provided for each AESI as well as any potential immune-mediated diseases (pIMDs), including number and percentage of participants with any event. In addition, summary will be provided by relationship to study intervention, maximum grade/severity, outcome, and the action taken. The worst-case approach will be applied at participant level for the maximum grade/severity, i.e., a participant will only be counted once as the worst case from all the events experienced by the participant.

The percentage of participants with at least 1 report of SAE (any, related, fatal and fatal related), and with at least 1 report of AESI respectively, classified by the MedDRA PT and SOC and reported from dosing up to study end and from D1 to D30 post-dose will be tabulated with exact 95% CI.

In the AESI/SAE summaries, a participant with 2 or more AEs within the same SOC or PT level but different relationship will be counted only once in the level using the related incident.

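### SAP 6.2.3.11 lets adverse events found only by four other cardiac SMQs enter the AESI summaries as myocarditis/pericarditis, while the protocol counts only the diagnosed condition

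*SAP*

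**What the plan says.** SAP 6.2.3.11 sets out how AESIs are found for analysis. For myocarditis/pericarditis it keeps the investigator's judgement and adds a search: "the following list of MedDRA SMQs will be used: Cardiac arrhythmia, Cardiac failure, Cardiomyopathy, Ischaemic heart disease, Non-infectious myocarditis/ pericarditis, narrow search". It closes with the inclusion rule for all AESI categories: "AESI summaries will include AE identified by either the investigator or the MedDRA queries".

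Elsewhere the SAP describes this AESI more narrowly. SAP 4.2.1.3 names the cardiac category simply as "Pericarditis and myocarditis" and states that "The summary of event characteristics will be provided for each AESI". The footnote to SAP Table 1 lists the same four AESI categories as the protocol and refers to Protocol Section 8.4.4 for them.

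Protocol 8.4.4.2 makes an event an AESI once there is enough evidence for the named diagnosis. Symptoms, signs or conditions that may or may not lead to it "should be recorded and reported as AEs but not as AESI until the final or definitive diagnosis has been made". Protocol 8.4.4.2.1 lists changes that suggest myocarditis or pericarditis, among them "Paroxysmal or sustained atrial or ventricular arrhythmias", and sends potential cases to an independent adjudication committee.

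SAP 4.9, which lists departures from protocol-defined analyses, contains one item, on RT-PCR at screening and Day 1.

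**The concern.** The inclusion rule is an either/or, so a query hit is enough by itself. Of the five SMQs, only the last is named for myocarditis and pericarditis. The others are named for arrhythmia, cardiac failure, cardiomyopathy and ischaemic heart disease. An adverse event with no diagnosis of myocarditis or pericarditis could therefore be shown under that label.

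This matters because AESIs up to Day 31 are part of the primary endpoint and AESIs up to Month 6 are a secondary endpoint. Both are tabulated as number and percentage with exact 95% CIs (SAP 4.2.1.1 and 4.3.1.1). Protocol 8.3.8 treats myocarditis and pericarditis as an important potential risk, so a reader will look closely at that line. With 18 vaccinees or 6 placebo recipients per group, a single event is visible.

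**Working it through.** **1. One event followed through both documents.** Take a participant whose Day 8 EKG shows an arrhythmia that the investigator judges clinically significant, with no diagnosis of myocarditis or pericarditis.

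- Is it an adverse event? Yes. Protocol 10.3.1 includes abnormal results of "other safety assessments (e.g., EKG, radiological scans, vital signs measurements), including those that worsen from baseline, considered clinically significant" in the investigator's judgement.
- Is it an AESI under Protocol 8.4.4.2? No. Arrhythmia is a suggestive change in Protocol 8.4.4.2.1, and the diagnosis has not been made.
- Is it in the AESI summaries under SAP 6.2.3.11? Yes, if its coded term falls in the Cardiac arrhythmia SMQ. The SMQ contents are not in the documents, so this step rests on the SMQ's name.
- Does any SAP section confine such a hit to case-finding, to adjudicated cases or to a separate table? None does.

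The documents allow this path to be traced for arrhythmia. For the other three SMQs the same reasoning rests on their names and on the either/or rule.

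**2. What one such event does to a table.** The plan states no figure on this point, so there is none to reproduce. Group sizes come from Protocol Tables 4 and 5:

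- vaccine dose group: 18
- each Part A placebo group and the Part B placebo group: 6
- Part A pooled placebo: 3 × 6 = 18
- combined placebo: 18 + 6 = 24
- combined 10 µg: 18 + 18 = 36

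The interval is Clopper-Pearson, as in SAP 4.1.1. For x events in n participants, the lower limit is the 2.5% point of Beta(x, n − x + 1) and the upper limit is the 97.5% point of Beta(x + 1, n − x). For x = 0 the lower limit is 0 and the upper limit is 1 − 0.025^(1/n); for n = 18 that is 1 − 0.025^(1/18) = 18.5%.

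| Group | n | No event (95% CI) | One query-only event (95% CI) |
|---|---|---|---|
| Single placebo group | 6 | 0% (0 to 45.9) | 16.7% (0.4 to 64.1) |
| Vaccine dose group, or Part A pooled placebo | 18 | 0% (0 to 18.5) | 5.6% (0.1 to 27.3) |
| Combined placebo | 24 | 0% (0 to 14.2) | 4.2% (0.1 to 21.1) |
| Combined 10 µg | 36 | 0% (0 to 9.7) | 2.8% (0.1 to 14.5) |

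The row for 6 is relevant because SAP 4.1.1 shows each Part A placebo group separately in safety tables.

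**3. How often it might happen.** The documents give no rate for events caught only by the four SMQs. As pure assumption, let the rate p be 0.5%, 1% or 2%. Planned vaccinees number 3 × 18 + 2 × 18 = 90. The expected number of hits is 90p = 0.45, 0.9 or 1.8. The chance of at least one in a group of 18 is 1 − (1 − p)^18 = 8.6%, 16.5% or 30.5%. The same formula gives 60.3% at p = 5%, which matches the sample-size statement in Protocol 9.2. These values show scale and are not an estimate.

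**The case against.** The strongest reply is that the two texts do different jobs. Protocol 8.4.4.2 tells investigators how to record and report an event, and SAP 6.2.3.11 tells the sponsor how to retrieve events for tables. Both can be followed at once. Protocol 9.4 leaves technical detail to the SAP, and Protocol 9.4.1 prescribes no retrieval method. Casting a wide net for a known risk is sensible, and the hypersensitivity and COVID-19 AESIs are also searched by SMQ.

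Part of this stands: the search is legitimate and should stay. It does not settle what its hits are called. The SAP's AESI definition points to Protocol 8.4.4, so the endpoint is the protocol's category. In the same SAP section the hypersensitivity query is fitted to its category by grade, narrow search and onset within 24 hours, whereas the cardiac query has no such tie to the diagnosis. It is unclear whether the narrow-search phrase governs all five SMQs or only the last, but the four others remain in the list either way.

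A reader might infer that the trial will report an inflated myocarditis rate, or that safety decisions could be misled. The documents do not support that:

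- No number of hits can be derived from them. Participants are 18 to 49, and exclusion criterion 10c removes clinically significant cardiovascular disease.
- The endpoint tables are classified by system organ class and preferred term, so an arrhythmia appears as an arrhythmia, and AESIs are listed in detail.
- There is no hypothesis test, and no holding rule in Protocol Table 12 uses the AESI count.
- Case determination runs through blinded independent adjudication (Protocol 8.3.8 and 8.4.4.2.1), which does not depend on the SAP query.

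**Conclusion.** The mismatch is real and limited. Read literally, SAP 6.2.3.11 lets events found only by four SMQs for other cardiac conditions be summarised as myocarditis/pericarditis. The protocol definition does not allow this, and SAP 4.9 does not declare it. The possible results are a mislabelled line in the per-AESI summary of SAP 4.2.1.3 and an AESI total that is too high in the primary and secondary safety tables. Each affected participant adds 5.6 percentage points in a group of 18 and 16.7 in a group of 6.

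The conclusion rests on two readings: that the either/or rule means what it says, and that SMQs named for other conditions contain terms for those conditions. Whether any total is actually over-counted depends on hits that may not occur. This is a wording fault worth correcting before the final tables are produced. It does not threaten the trial's conclusions.

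**What to change.** In SAP 6.2.3.11 and 4.2.1.3, count an event as the myocarditis/pericarditis AESI only if one of these holds:

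- the investigator identified it as myocarditis or pericarditis;
- the independent adjudication committee confirmed it;
- its reported term is itself myocarditis or pericarditis.

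Protocol 8.4.4.2.1 speaks of probable and definitive cases after adjudication, so the SAP should state which of these count as confirmed.

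Keep the other four SMQs as a case-finding search. Report events that only they identify in a separate table with a plain label, such as potential cases identified by query, and leave them out of the AESI subtotal and total. Those with onset in the 30-day period remain in the unsolicited adverse event tables, so they are not lost from the primary analysis.

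If the wider rule is intended, declare it in SAP 4.9 and label the row for what it contains.

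The cost is a few lines of SAP text and one extra table. No new data are needed, and investigator reporting does not change.

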## 8.4.4.2.2. SARS-CoV-2 infection and COVID-19 definitions and assessment

Vaccine efficacy will not be evaluated in this study, but all laboratory-confirmed asymptomatic SARS-CoV-2 infections should be reported by the participant and documented as AEs, while virologically confirmed cases of COVID-19 are reported as AESIs. Any available isolate genotyping results will also be requested. Participants will be instructed to inform the investigator in the event of a positive SARS-CoV-2 diagnostic test. Serology testing for SARS-CoV-2 N protein will be performed pre-vaccination and post-vaccination to monitor for undetected SARS-CoV-2 infections at the time points specified in the SoA (Section 1.3).

All participants with suspected COVID-19 are required to have an unscheduled visit for suspected COVID-19, as detailed in the SoA (Section 1.3). At this visit, participants will undergo the following assessments:

- Medical history
- SARS-CoV-2 RT-PCR (nasopharyngeal or mid-turbinate swab)
- Physical examination
- Vital sign measurements
- Body temperature
- Review of AEs
- Concomitant medication/vaccination

All participants with confirmed COVID-19 are required to have an unscheduled COVID-19 convalescent visit as detailed in the SoA (Section 1.3). At this visit, participants will undergo the following assessments:

- Medical history
- SARS-CoV-2 RT-PCR (nasopharyngeal or mid-turbinate swab)

- Physical examination
- Vital sign measurements
- Body temperature
- COVID-19 evaluation
- Review of AEs
- Concomitant medication/vaccination

To complete the COVID-19 evaluation, the investigator will review the history of the participants, including medical records to define the severity of COVID-19.

Any confirmed cases of SARS-CoV-2 infection or COVID-19 during the study will be assigned one of the following definitions and recorded in the eCRF:

Asymptomatic SARS-CoV-2 infection:	Laboratory-confirmed SARS-CoV-2 by RT-PCR or SARS-CoV- 2 N protein seroconversion without any of the following symptoms: fever or chills, cough, shortness of breath or difficulty breathing, fatigue, muscle or body aches, headache, new loss of taste or smell, sore throat, congestion or runny nose, nausea or vomiting, diarrhea		

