COVID-19:	Virologically confirmed SARS-CoV-2 by RT-PCR with 1 or more of the following symptoms: fever or chills, cough, shortness of breath or difficulty breathing, fatigue, muscle or body aches, headache, new loss of taste or smell, sore throat, congestion or runny nose, nausea or vomiting, diarrhea		
Severe COVID-19:	Virologically confirmed SARS-CoV-2 infection with any 1 of the following:		
	• Clinical signs at rest indicative of severe systemic illness (respiratory rate ≥ 30 per minute, heart rate ≥ 125 per minute, SpO2 ≤ 93% on room air at sea level or PaO2/ FiO2 < 300 mm Hg)		
	• Respiratory failure (defined as needing high-flow oxygen, non-invasive ventilation, mechanical ventilation, or ECMO)		
	• Evidence of shock (systolic blood pressure <90 mmHg, diastolic blood pressure <60 mmHg, or requiring vasopressors)		
	• Significant acute renal, hepatic, or neurologic dysfunction		
	• Admission to a hospital or an intensive care unit		
	• Death		

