# 4.6. Other Safety Analysis

## 4.6.1. COVID-19 Assessment and COVID-19 AEs

A participant with an AE of SARS-CoV-2 infection can be categorized as "Asymptomatic SARS-CoV-2 infection", "COVID-19" or "Severe COVID-19" to the case diagnosis question from the COVID-19 coronavirus infection assessment electronic Case Report Form (eCRF).

Any case of "COVID-19" or "Severe COVID-19" is an AESI; and will be captured and described.

The listing of participants with any category of SARS-CoV-2 infection will be provided based on the Exposed Set.

The listing of participants who had a COVID-19 test performed with their results will be provided on the Exposed Set.

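### The SAP's derivation of the 'virologically confirmed COVID-19' AESI accepts any adverse event under the COVID-19 MedDRA query, with no RT-PCR, symptom or eCRF-category condition, so nothing in it keeps asymptomatic infections out

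*SAP*

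**What the plan says.** **The derivation.** SAP 6.2.3.11 lists how each AESI is identified. For virologically confirmed COVID-19 it starts from the investigator's judgement and adds that "AEs under MedDRA SMQ COVID-19, narrow search will be used". The section ends: "AESI summaries will include AE identified by either the investigator or the MedDRA queries". The two sources are therefore joined as a union. In the same list the hypersensitivity query does carry clinical conditions: "Grade 3 unsolicited AEs under MedDRA SMQ hypersensitivity, narrow search (includes anaphylaxis), with an onset within 24 hours after dosing". The COVID-19 query carries none.

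**The definition.** Protocol 8.4.4.2.2 separates infection from disease. It says that "all laboratory-confirmed asymptomatic SARS-CoV-2 infections should be reported by the participant and documented as AEs", and that virologically confirmed COVID-19 is what is reported as an AESI. COVID-19 itself is defined there as "Virologically confirmed SARS-CoV-2 by RT-PCR with 1 or more of the following symptoms". Asymptomatic infection is a separate category, established by RT-PCR or by N protein seroconversion without any listed symptom. Protocol 8.4.4.2 adds that events that might or might not lead to an AESI diagnosis "should be recorded and reported as AEs but not as AESI until the final or definitive diagnosis has been made".

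**The rest of the SAP.** SAP 4.2.1.3 ties this AESI to Protocol 8.4.4.2.2. SAP 4.6.1 describes three eCRF categories (asymptomatic infection, COVID-19, severe COVID-19) and says that a case in either of the last two "is an AESI; and will be captured and described"; it does not say this of the first. SAP 4.9, on changes to protocol-defined analyses, mentions no broadening of the AESI.

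**The concern.** The name of the category and the rule that fills it do not match. The name requires virological confirmation, and the protocol definition behind it also requires a symptom. The rule requires only that the AE's coded term be in the query.

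The trial is likely to produce the records that could be affected. After dosing it swabs every participant at Day 8 and Day 15, and it tests N serology at Day 15, Day 31 and Month 6 (Protocol 1.3, Table 1). The protocol then asks for laboratory-confirmed asymptomatic infections to be documented as AEs. The clearest example is a participant without symptoms who has a positive swab at the Day 15 visit, recorded as an AE. Under Protocol 8.4.4.2.2 and SAP 4.6.1 this is not an AESI. Under SAP 6.2.3.11 it becomes one if its coded term is in the query.

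At stake is the accuracy of a primary safety table (AESIs to Day 31) and of the secondary table to Month 6. With 18 participants per vaccine group, a single record is visible in the percentage.

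**Working it through.** The plan states no figure for this point, so there is none to reproduce. The check compares the texts and then sizes the effect.

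**1. Texts side by side, for an asymptomatic RT-PCR-positive participant recorded as an AE**

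| Source | Condition for this AESI | AESI? |
|---|---|---|
| Protocol 8.4.4.2.2 | RT-PCR positive and at least one listed symptom | No |
| SAP 4.2.1.3 | As Protocol 8.4.4.2.2 | No |
| SAP 4.6.1 | eCRF category COVID-19 or severe COVID-19 | Not named as one |
| SAP 6.2.3.11 | Investigator judgement, or coded term in the query | Yes, if the term is in the query |

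The same holds for N seroconversion without symptoms, provided that the site records it as an AE. No other SAP section filters the query hits. The allowance in SAP 6.2.3.11 for revising the queries refers to the MedDRA dictionary and adds no confirmation step.

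**2. Effect of one misclassified record on a group**

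Inputs: 18 per vaccine group (SAP 5); 18 + 18 = 36 in the pooled 10 µg group; Clopper-Pearson intervals (SAP 6.2.5.1). For x of n, the lower limit is the 2.5% quantile of Beta(x, n-x+1), and the upper limit is the 97.5% quantile of Beta(x+1, n-x).

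| Group size | No true case | One record added |
|---|---|---|
| 18 | 0% (0-18.5) | 5.6% (0.1-27.3) |
| 36 | 0% (0-9.7) | 2.8% (0.1-14.5) |

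Two records in a group of 18 give 11.1% (1.4-34.7).

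**3. How many such records**

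The documents give no attack rate. Assumptions: 10-20% of participants infected over six months, spread evenly, and 30-50% of those asymptomatic or unconfirmed. Participants: 72 + 42 = 114. General AEs are collected only until Visit 4, Day 31 (Protocol 8.4.1), so about 30 of 180 days count.

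- Infections by Day 31: 114 × 10% × 30/180 = 1.9, up to 114 × 20% × 30/180 = 3.8.
- Asymptomatic or unconfirmed: 1.9 × 30% = 0.6, up to 3.8 × 50% = 1.9 participants.
- As a share of 114: about 0.5-1.7%.
- Chance of at least one in a given group of 18: 1 - 0.995^18 = 8.6%, up to 1 - (1 - 0.0167)^18 = 26%.

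These are upper bounds in one respect: they take every such record to have a coded term inside the query. They also include unconfirmed cases, whose status the protocol leaves unsettled.

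**The case against.** **Broad capture is a deliberate safety net.** The myocarditis/pericarditis entry in the same list also adds queries to investigator judgement, and over-inclusion is the cautious direction for safety. That is a fair reading of the intent. It does not justify the label: a hit can be kept in view without being tabulated as virologically confirmed.

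**The reader can largely undo it.** AESIs are tabulated by preferred term. The SAP lists AESIs, all infection categories and all COVID-19 test results (SAP 4.2.1.1 and 4.6.1), and SAP 4.4.3 separately summarises RT-PCR-confirmed infection reported as AESI. There is no hypothesis test, and no holding rule in Protocol Table 12 is triggered by an AESI as such. All of this stands and limits the consequence. The headline AESI percentage would still be wrong under the protocol's definition.

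**The query's content is unknown.** This stands. A reader might infer that asymptomatic infections will enter the primary endpoint. The documents do not list the query's terms, so they show only that the rule does not keep such infections out.

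**The protocol itself has a broader definition.** The risk table in Protocol 2.3 treats suspected and probable cases as AESIs too, and the note under Table 1 refers to WHO case definitions. A reader might infer that counting a symptomatic home-test-positive case with a negative RT-PCR is a plain SAP error. The documents do not support that: Protocol 2.3 points one way, while the Table 3 footnote, 8.4.4.2 and 8.4.4.2.2 point the other. This is a contradiction within the protocol. Protocol 2.3 does not clearly cover asymptomatic infection, so it does not answer the main point.

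**Conclusion.** The concern holds in a conditional form. SAP 6.2.3.11 would count as a virologically confirmed COVID-19 AESI any AE whose term is in the query, including asymptomatic infections that Protocol 8.4.4.2.2 keeps as AEs and SAP 4.6.1 does not name as AESIs.

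Each such record adds 5.6 percentage points in a vaccine group of 18. The number is likely small: about 0.6-1.9 of 114 participants, given the assumed attack rate, even spread, assumed asymptomatic or unconfirmed share and Day 31 cut-off.

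A reader might apply the six-month attack rate to everyone and reach 114 × 10% × 30% = 3 to 114 × 20% × 50% = 11 participants, or 3-10 percentage points. The documents do not support that scale, because general AE collection stops at Day 31 and scheduled post-dose swabs at Day 15. Some later records remain possible: medically attended and serious events are collected to Month 6, and Protocol 8.4.4.2.2 sets no end date for infection reports. Nor would every added case lack both symptoms and RT-PCR confirmation; the Day 15 example is RT-PCR positive.

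The defect is in the case definition of a descriptive safety table. It is worth correcting because the mismatch is plain and the repair is cheap.

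**What to change.** In SAP 6.2.3.11, count a query hit as this AESI only if its eCRF category is COVID-19 or severe COVID-19 (SAP 4.6.1) and it is RT-PCR confirmed (Protocol 8.4.4.2.2). Both conditions need to be written out, because SAP 4.6.1 relies on the eCRF category and states no RT-PCR condition of its own. Show the remaining query hits on a separate line outside the AESI total, and query those without a category with the site.

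Separately, reconcile the protocol passages on suspected, probable and unconfirmed cases: the risk table in 2.3 against the Table 3 footnote, 8.4.4.2 and 8.4.4.2.2. If the broader definition is the intended one, the label in SAP 6.2.3.11 and the wording of SAP 4.6.1 must change to match.

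The SAP change costs one bullet and a merge with RT-PCR and eCRF data that are already collected. The reconciliation needs a protocol clarification, which the SAP edit does not replace.
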